## LIST OF ABBREVIATIONS

Term	Definition
AE	Adverse Event
CFR	Code of Federal Regulations
CMV	Cytomegalovirus
CRF	Case Report Form
CTCAE	Common Terminology Criteria of Adverse Event
CV%	Coefficient of Variance
DCD	Donors after Cardiac Death
ECD	Expanded Criteria Donor
eCRF	Electronic Case Report Form
eGFR	estimated Glomerular Filtration Rate
FDA	Food and Drug Administration
GCP	Good Clinical Practice
GFR	Glomerular Filtration Rate
ICF	Informed Consent Form
ICH	International Conference on Harmonization
IRB	Institutional Review Board
ITT	Intent-to-Treat
msec	Millisecond
mTOR	Mammalian Target of Rapamycin
NPO	Nothing by Mouth (Nil Per Os)
PCP	Pneumocystis Carinii Pneumonia
PCR	Polymerase Chain Reaction
POD	Post Operative Day
QTc	QT interval
R	Research
SAE	Serious Adverse Event
SCD	Standard Criteria Donor
SOC	Standard of Care
TMHRI	The Methodist Hospital Research Institute

## STUDY SYNOPSIS

SPONSOR / PRINCIPAL INVESTIGATOR	The Methodist Hospital Research Institute / A. [name]
TITLE:	Ciprofloxacin for Prevention of BK Infection in Renal Transplant Recipients
OBJECTIVES:	
The primary objective of this study is
 
 
• To evaluate the efficacy of routine ciprofloxacin administration post-transplantation for the reduction of the incidence of BK infection in renal transplant recipients
 
 
Secondary objectives include:
 
 
• To evaluate the safety and tolerability of routine ciprofloxacin administration in kidney transplantation
 

TRIAL DESIGN:	The proposed study is a single-center, randomized, prospective, double-blind, placebo-controlled study
TYPE AND NUMBER OF SUBJECTS:	The study will be comprised of 180 kidney transplant subjects
RANDOMIZATION	2:1 study regimen to comparator group
STUDY REGIMEN	Ciprofloxacin 500 mg (dispensed as two-250 mg capsules) once daily for up to 90 days post-transplant
COMPARATOR REGIMEN	Placebo, dispensed as two-matching capsules, once daily for up to 90 days post-transplant
Main Inclusion criteria	
 
1. Male or female subjects over the age of 18 years
 
2. Recipients of a primary or repeat renal allograft either alone (from a deceased or living donor) or as a dual-kidney transplant
 
3. Signed informed consent form prior to any research assessment
 

Main Exclusion criteria	
 
1. Patients with known severe allergy to ciprofloxacin
 
2. History of tendon rupture or tendinitis
 
3. Use of antiarrhythmic drugs known to prolong the QT interval such as class IA antiarrhythmic drugs (e.g. quinidine, procainamide, disopyramide), class III antiarrhythmic drugs (e.g. amiodarone, sotalol)
 
4. Patients with history of previous non-renal transplantation
 
5. Recipients administered rituximab within one year prior to transplantation, or recipients expected to receive rituximab as part of desensitization strategy or for the presence of historical donor specific antibodies
 
6. Any condition present during the initial transplant hospitalization that in the investigator's judgment would increase the risk associated with participation in the study
 
7. QTc interval of greater than 500 msec on admission or post-operative EKG
 
8. BK nephropathy with previous transplant
 
9. BK viremia on admission
 

TRIAL AND TREATMENT DURATION:	
 
• 24 month enrollment + 12 month follow-up
 
• 3 month treatment duration
 

## 1 Introduction

### 1.1 Background

BK virus is a member of the virus family polyomaviridae (“polyoma”). The virus, which can manifest as a viral nephritis, was first described in a renal transplant recipient in 1971, however it was not until the past decade that infection with BK virus became known as an important contributor to graft dysfunction and graft loss after renal transplantation. It has been widely accepted that emergence of BK virus correlates with the more potent immunosuppressive agents currently used to lower acute rejection rates ([1] Brennan et al. Am J Transpl 2005; 5(3):583-94). In contrast to other opportunistic infections after transplantation, for which routine prophylactic agents are administered, there is no effective agent for the prevention of BK infection, nor is there an effective agent for treating BK infection once it occurs.

Ciprofloxacin is a well known anti-infective agent in the fluoroquinolone class of antibiotics. It is most active against gram-negative enteric pathogens, and is commonly used for a variety of infectious indications.

Though classified as antibacterial agents, fluoroquinolones have been suggested to exhibit anti-BK viral effects by interfering with helicase activity of the BK virus large T antigen ([2] Ali et al. Antivir Ther 2007; 12:1-6). Ciprofloxacin has been shown in previous studies to reduce urine BK viral load ([3] Leung et al. Clin Infect Dis 2005; 40:528), and BK-associated hemorrhagic cystitis ([4] Miller et al. Biol Blood Marrow Transplant 2011) in the stem cell transplant population. Ciprofloxacin has also been associated with a lower incidence of BK viremia in one retrospective study in kidney transplant recipients ([5] Gabardi et al. Clin J Am Soc Nephrol 2010; 5: 1298). Based on these reports, we hope to find a reduction BK viremia and BK nephropathy using a prospective, randomized study design.

## 2 Purpose and objectives

### 2.1 Purpose

The purpose of this study is to evaluate the safety and efficacy of ciprofloxacin for the prevention of BK infection in renal transplant recipients.

### 2.2 Objectives

#### 2.2.1 Primary objective

To determine whether routine ciprofloxacin administration post-transplantation can lower the incidence of BK infection in renal transplant recipients

#### 2.2.2 Secondary objective

To evaluate the safety and tolerability of routine ciprofloxacin administration in kidney transplantation with respect to:

- Incidence of adverse events
- Incidence of urinary tract infections as defined by a midstream urine sample containing  $10^4$  or more colony-forming units per mL
- Incidence of quinolone-resistant urinary tract and bloodstream infections
- Incidence of *Clostridium difficile* infections
- Incidence and severity of BK nephropathy
- Time to onset of and quantitation of BK viremia
- Graft outcomes

### **3 Design Rationale**

The proposed study is a randomized, prospective, double-blind, placebo-controlled study. The rationale for a placebo-controlled arm is that there are no established preventative strategies for BK infection. Currently, there are no prospective studies evaluating preventative or treatment agents for BK infection.

### **4 Experimental Plan**

#### **4.1 Study Design**

This is a single-center, randomized, prospective, double-blind, placebo-controlled study. Eligible subjects who enroll in this study will be randomized prior to discharge from the initial transplant hospitalization in a 1:2 ratio standard of care (placebo), or 90 days of once-daily ciprofloxacin. Patients will be stratified based on the use of alemtuzumab (Campath) induction.

##### **4.1.1 Study Endpoints**

###### **4.1.1.1 Primary Endpoint**

The primary endpoint will be the proportion of patients developing BK infection at 6 months post-transplant. BK infection is defined as the presence of a detectable BK viral load in plasma by polymerase chain reaction (PCR), or the presence of BK viral inclusions on kidney biopsy specimens. All detectable PCRs must be confirmed by repeat PCR to be considered positive.

###### **4.1.1.3 Additional Evaluations to be Tracked**

The following safety parameters will be assessed and measured during the study period:

- Dose discontinuation due to adverse event related to therapy
- Serum creatinine concentrations at 1, 3, 6, 9, and 12 months post-transplant
- Graft loss at 1 year
- Death at 1 year

#### **4.1.2 Number of Subjects**

A total of 180 kidney transplant recipients will be enrolled.

#### **4.1.3 Study Duration**

The study will begin at the time of transplant and subjects will be enrolled for 12 months post-transplant.

#### **4.1.4 Study Population**

Patients with end stage renal disease who are receiving a kidney transplant and who satisfy the following criteria will be considered for participation in this study.

##### **4.1.4.1 Inclusion Criteria**

1. Male or female subjects over the age of 18 years
2. Recipients of a primary or repeat renal allograft either alone (from a deceased or living donor) or as a dual-kidney transplant
3. Signed informed consent form prior to any research assessment

##### **4.1.4.2 Exclusion Criteria**

1. Patients with known severe allergy to ciprofloxacin
2. History of tendon rupture or tendinitis
3. Use of antiarrhythmic drugs known to prolong the QT interval such as class IA antiarrhythmic drugs (e.g. quinidine, procainamide, disopyramide), class III antiarrhythmic drugs (e.g. amiodarone, sotalol)
4. Patients with history of previous non-renal transplantation
5. Recipients administered rituximab within one year prior to transplantation, or recipients expected to receive rituximab as part of desensitization strategy or for the presence of historical donor specific antibodies
6. Any condition present during the initial transplant hospitalization that in the investigator's judgment would increase the risk associated with participation in the study
7. QTc interval of greater than 500 msec on admission or post-operative EKG
8. BK nephropathy with previous transplant
9. BK viremia on admission

## **5 Treatment Procedures**

### **5.1 Ciprofloxacin**

#### **5.1.1 Test Article and Administration**

The test article is defined as ciprofloxacin, and is supplied as 250 mg capsules by the sponsor. Matching placebo capsules will also be supplied by the sponsor.

In order to maintain blinding among subjects and investigators, study medication will be dispensed in pre-fill containers of 200 capsules each and labeled as "ciprofloxacin/placebo".

#### **5.1.2 Dosage and Administration**

The dosages of ciprofloxacin/placebo will be 500 mg daily, i.e. two of the 250 mg capsules once daily. This can be administered in the morning or in the evening. All study medication should be administered at least 1 hour prior to or 2 hours after administration of any antacid,

multivitamin, or other medications that contain divalent or trivalent cations (i.e. magnesium or calcium-containing supplements).

### **5.1.3 Dose Adjustments**

#### **5.1.3.1 Renal Dose Adjustments**

In patients with an estimated glomerular filtration rate of less than 30 ml/min/1.73m^2, dosing of ciprofloxacin/placebo should be reduced to 1 capsule once daily.

### **5.1.4 Dose Interruptions**

#### **5.1.4.1 Dose Interruptions**

In situations where holding of the study drug is required (i.e. patient is NPO or patient requires treatment with fluoroquinolone antibiotic as described in section 5.1.4.2), study drug can be held for up to 14 days. After 14 days of being off study drug, the investigator may consider withdrawing the subject from the study.

#### **5.1.4.2 Concomitant Antibiotics**

All infectious complications or conditions requiring antibiotic administration will be managed per routine standards. In cases where ciprofloxacin or alternative quinolone can be administered as a treatment option, study drug should be held during administration for the appropriate duration. Upon completion of treatment the study drug can be resumed for remainder of study duration. If the study drug is held longer than 14 days the investigator may consider withdrawing the subject from study. In cases where an alternate class of medication is deemed necessary, the study drug should be continued throughout the duration of concomitant antibiotic use.

#### **5.1.4.3 Development of BK Viremia**

Subjects who develop BK viremia or BK nephropathy will be managed according to the center's routine protocol. Except in the case of an SAE, study drug should continue for the remainder of its specified course.

## **5.2 Concomitant Immune Suppression**

All patients are required to remain on concomitant maintenance immune suppression therapies, including at least 2 of the following agents: calcineurin inhibitors, antimetabolites, or mTOR inhibitors.

### **5.2.1 Calcineurin Inhibitors**

#### **5.2.1.1 Tacrolimus (Prograf)**

Tacrolimus (Prograf) dosages are administered every 12 hours and adjusted to target 12-hour trough concentrations of 5 – 15 ng/mL.

#### **5.2.1.2 Cyclosporine**

Cyclosporine modified dosages are administered every 12 hours and are adjusted to target 12-hour trough concentrations of 150 – 250 ng/mL.

## 5.2.2 mTOR Inhibitors

### 5.2.2.1 *Sirolimus (Rapamune)*

Sirolimus (Rapamune) dosages are administered once daily and adjusted to target 24-hour trough concentrations of 5 – 10 ng/mL.

When combined with tacrolimus, sirolimus and tacrolimus concentrations will be adjusted to maintain a total combined level of 8-12 ng/mL.

## 5.2.3 Antimetabolites

### 5.2.3.1 *Mycophenolate Mofetil (Cellcept)*

Mycophenolate mofetil (Cellcept) will be administered to target a cumulative dosage of 1000 to 2000 mg per day. Dosages may be reduced for common adverse effects such as gastrointestinal intolerance or leukopenia.

## 5.2.4 Induction agents

Induction therapy will be determined by the prescriber based on the centers standard of care protocol.

5.2.4.1 Patients will be stratified upon enrollment based on alemtuzumab induction.

## 5.2.5 Corticosteroids

All patients will receive intraoperative intravenous methylprednisolone, which will be tapered to an oral prednisone dosage at discharge. Long-term maintenance steroid use will be determined by the prescriber based on the centers standard of care protocol..

## 5.3 Study Drug Handling

Drug inventory and accountability records for the study drugs will be kept by the investigator/pharmacist. Study drug accountability throughout the study must be documented. The following guidelines are therefore pertinent:

- The investigator agrees not to supply study drugs to any persons except the subjects in this study.
- The investigator/pharmacist will keep the study drugs in a pharmacy or other locked and secure storage facility under controlled storage conditions, accessible only to those authorized by the investigator to dispense these test drugs.
- A study drug inventory will be maintained by the investigator/pharmacist. The inventory will include details of when they were dispensed and to which subject.
- At the conclusion or termination of this study, the investigator/pharmacist agrees to conduct a final drug supply inventory and to record the results of this inventory on the Drug Accountability Record.
- Used or unused study drug may be destroyed at the study center according to standard institutional procedures after drug accountability has been conducted. A copy of the standard institutional procedure for destroying investigational drugs will be provided to the Sponsor or designee upon request. Unused study drug not destroyed at the site must be returned to the Sponsor or designee at the end of the study or upon expiration.

## **6 Study Procedures**

### **6.1 Consent Process**

After approval by The Methodist Hospital Research Institute's Institutional Review Board, the Principal Investigator, or a designated member of his study team, will approach potential subjects prior to transplantation regarding participation in the study. The study will be described by explaining the purpose of the study, the methods and objectives, and the potential risks associated with the study. An informed consent form (ICF) will be provided. Patients will be given time to read the ICF, and will be allowed to ask questions about the study. They will be informed that their participation is voluntary and that choosing not to be involved will not influence their care at The Methodist Hospital. They will be informed that they may choose to withdraw from the study at anytime for any reason. Subjects will be given an ICF to keep. The informed consent process will be documented in the patient's chart.

Any new information about the study medications that may be provided by the manufacturer or the Food and Drug Administration will be provided to the Institutional Review Board. Subjects will also be provided this information through a revised ICF and will be given the opportunity to decide whether or not to continue in the study.

### **6.2 Assessment of Eligibility**

At the time of transplant or, if possible, up to 14 days prior to transplant, the subject may be approached regarding potential interest in study involvement. Their medical history will be reviewed to assess for eligibility. Prior to performing any research-related procedures, informed consent will be obtained. Subjects must meet all inclusion criteria and none of the exclusion criteria or enrollment into the study will not be possible.

### **6.3 Enrollment**

Subjects who qualify for enrollment in this study after signing informed consent will be enrolled, and proceed into the study at the time of transplantation.

### **6.4 Procedures**

#### **6.4.1 Pre-treatment Data Collection**

BK PCR from plasma will be collected during the initial hospital visit prior to study drug administration (per standard of care). Study drug will be initiated upon discharge from initial hospitalization, and no later than day 7 post-transplant.

#### **6.4.2 Post-treatment Data Collection**

Patients will remain on study medication for 90 days post-transplant. All routine standard of care procedures/visits will apply. Patients are to have routine BK PCR drawn at 1, 2, 3, 6, 9, and 12 months post-transplant. Study visits will occur at baseline, 2 weeks, and 1, 2, 3, 6, 9, and 12 months post-transplant.

### **6.5 Standard Laboratory Tests**

At transplantation, prior to the transplant surgery, the following tests are routinely performed: Hematology and a Comprehensive metabolic panel (chemistry) (described below in Section 6.5.1). Daily hematology and chemistry are performed during hospitalization and upon discharge. A schedule of follow-up visits include basic hematology and chemistry assessments that will be recorded in the clinical record and in the study record. See Section 6.5.1 Sequence of events below for detail.

### 6.5.1 Sequence of Events

Time of Visit	Screening/Baseline -14 to 7 days post transplant	2 Weeks Post TXP	1 Month Post TXP	2 Months Post TXP	3 Months Post TXP	6 Months Post TXP	9 Months Post TXP	12 Months Post TXP
Visit Window	N/A	±7 Days	± 7 Days	± 7 Days	± 14 Days	±14 Days		
Visit Number	1	2	3	4	5	6	7	8
Inclusion/Exclusion criteria	X (R)							
Informed consent	X (R)							
Med History 	X (R)							
Concomitant Medications 	X (R)	X (R)	X (R)	X (R)	X (R)	X (R)	X (R)	X (R)
Transplant Data Collection 	X (R)							
Randomization 	X (R)							
Study Medication Dispensation or Return	X (R)	X (R)	X (R)		X (R)			
Study medication record	X (R)	X (R)	X (R)		X (R)			
BK PCR (serum)	X (SOC)		X (SOC)	X (SOC)	X (SOC)	X (SOC)	X (SOC)	X (SOC)
AE/SAE Assessment	X (R)	X (R)	X (R)	X (R)	X (R)			
Serum Creatinine	X (SOC)		X (SOC)		X (SOC)	X (SOC)	X (SOC)	X (SOC)
Urine Analysis and culture (if applicable) and blood cultures	X (SOC)	X (SOC)	X (SOC)	X (SOC)	X (SOC)	X (SOC)		
Tacrolimus/Sirolimus levels	X (SOC)	X (SOC)	X (SOC)	X (SOC)	X (SOC)	X (SOC)	X (SOC)	X (SOC)
Urine Protein to Creatinine Ratio			X (SOC)	X (SOC)	X (SOC)	X (SOC)	X (SOC)	X (SOC)

### 6.5.2 Screening and Eligibility

Between day -14 and day 7 post-transplant after obtaining informed consent, subjects who fulfill all of the inclusion criteria and none of the exclusion criteria will be enrolled into the study. Documentation of the fulfillment of criteria will be included in the study files.

 Medical history includes history of age, diagnosis for renal failure, history of diabetes, duration and type of dialysis, cytomegalovirus (CMV) serology, and HLA typing.

 Immunosuppressant medications, including medications used to treat rejection, and concomitant anti-microbial use will be captured. At months 6,9 and 12 only immunosuppressant dosages are required.

. Transplant information includes donor demographics (age, sex, race) and CMV serology, donor history (terminal serum creatinine, cause of death), type of transplant (ECD, DCD, or SCD), ischemia times, peak PRA and most recent PRA prior to transplant.

 Subject must meet all Inclusion and Exclusion Criteria prior to randomization.

### **6.5.3 Study Completion**

Subjects who attend the 12-month study visit and have completed all study-related evaluations described in Section 6.5.1 will be considered as having completed the study.

Subjects who elect to discontinue pre-maturely or are withdrawn from the study by the investigator, will be converted to standard of care treatment, will return any unused study drug, and will be asked to attend a final end-of-study safety evaluation visit. If it is not possible to complete the end-of-study visit, every attempt will be made to determine safety endpoints (adverse events, rejection, graft loss or death information) occurring since the previous visit. A phone visit may be utilized for this information if the subject is unable or unwilling to attend the end-of-study visit.

Subjects will be followed as standard of care after the study regimen has been completed or discontinued. Standard of care may include the continued monitoring of BK PCRs.

## **7 Blinding**

### **7.1 Blinding Method**

This is a double-blind, randomized, prospective study. Subjects will be assigned to a double-blind treatment arm in the order in which they meet the criteria for randomization. The pharmacist will be unblinded to treatment. All other study site staff and all members will remain blinded to treatment arm except as described below.

### **7.2 Retention of the Assignment Schedule and Procedure for Treatment Code Breaking**

The randomization schedule will be stored in the Site Pharmacy holding area. Study drug treatment may be revealed only for reasons relating to the subject's safety and when critical therapeutic decisions are contingent on knowing the assigned study drug. Withdrawal of a subject from the study is not a sufficient reason to break the study blind. If the blind is broken for a subject, the reason is to be documented as a written entry in the source document.

## **8 Statistical Analysis Plan**

### **8.1.1 Data Analysis**

A full analysis will be conducted based on the intent-to-treat (ITT) population. The ITT population will be defined as all randomized subjects who take at least one dose of the assigned therapy after randomization. A per-protocol analysis will be performed on all randomized patients completing 90 days of study drug. The primary endpoint of the difference in proportion of patients developing BK infection within 6 months will be determined using the chi-square test. All secondary and safety outcomes will be analyzed using chi-square or fisher exact testing for categorical variables, and analysis of variance or t-tests for continuous variables. Time to BK infection and graft survival will be estimated using Kaplan-Meier methodology. Univariate and multivariate proportional hazards Cox models will be developed to determine the risk factors of study outcomes.

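### Patients off study drug can be withdrawn from the study without a 6-month BK outcome, and no rule covers the gap; the set labelled ITT also requires a dose

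*Combined protocol and SAP*

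**What the plan says.** **Analysis sets and test (8.1.1).** "A full analysis will be conducted based on the intent-to-treat (ITT) population", and the set is defined so: "The ITT population will be defined as all randomized subjects who take at least one dose of the assigned therapy after randomization". The only other set is narrower: "A per-protocol analysis will be performed on all randomized patients completing 90 days of study drug". The test is given as: "The primary endpoint of the difference in proportion of patients developing BK infection within 6 months will be determined using the chi-square test". The section does not say which set is primary for this endpoint, and it has no rule for a subject whose 6-month BK status is unknown.

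**Randomization and first dose.** Under 4.1, subjects are "randomized prior to discharge from the initial transplant hospitalization". Under 6.4.1: "Study drug will be initiated upon discharge from initial hospitalization, and no later than day 7 post-transplant".

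**Leaving the study.** Section 5.1.4.1 says: "After 14 days of being off study drug, the investigator may consider withdrawing the subject from the study". Section 5.1.4.2, on treatment with ciprofloxacin or another quinolone, repeats it: "If the study drug is held longer than 14 days the investigator may consider withdrawing the subject from study".

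**Follow-up afterwards.** Section 9.2.1 gives 30 days from the last dose as the follow-up for a subject who stops study drug. Section 6.5.3 asks a withdrawn subject for one final safety visit. If that fails, the data to be sought are adverse events, rejection, graft loss and death; BK PCR is not among them. The same section mentions later BK PCR monitoring only as something that standard of care might include.

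**Planned BK PCR.** Sections 6.4.2 and 6.5.1 schedule it at months 1, 2, 3, 6, 9 and 12, as standard of care. None is scheduled at the 2-week visit.

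**The concern.** There are two linked defects of unequal weight.

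The minor one is the label. A set conditioned on taking a dose is modified ITT. Randomization comes before the first dose, so a patient can be randomized, never start, and drop out of every analysis set in the plan.

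The main one is that stopping drug can turn into leaving the study before the primary endpoint is measured. The chi-square test needs a yes or no for each subject. Without a rule, a withdrawn subject with no earlier infection is either dropped from the denominator or silently counted as uninfected. The two choices give different answers, and the choice could be made after the data are seen.

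Blinding does not guarantee that this loss is balanced. One named reason for holding drug is quinolone treatment of an infection. The study drug is itself an antibacterial, and urinary and bloodstream infections are secondary endpoints, so assignment may affect who is held and then withdrawn.

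**Working it through.** The plan gives no figure to reproduce: 180 subjects are stated without alpha, power, event rates, effect size or dropout. The documents supply 180 subjects at 2:1 (120 ciprofloxacin, 60 placebo), 90 days of treatment, 30 days of follow-up after the last dose, and a 6-month endpoint. Every event rate, withdrawal rate and the two-sided 5% level below is an assumption.

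**1. Timing.** Drug ends by about day 90. Then 90 + 30 = day 120 at the latest, and 180 − 120 = 60. The follow-up stated in 9.2.1 can therefore end about 60 days before the primary endpoint, and sooner for anyone who stops drug early.

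**2. How much unknown outcomes could matter.** With m subjects of unknown status per arm, the worst-case range of the risk difference has width m(cipro)/120 + m(placebo)/60.
- 2% unknown: 2/120 + 1/60 = 3.3 points
- 5% unknown: 6/120 + 3/60 = 10 points
- 10% unknown: 12/120 + 6/60 = 20 points

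**3. Fragility of one assumed result** (Pearson chi-square, no continuity correction).
- 12/60 against 10/120: p = 0.024
- two uncounted ciprofloxacin infections, 12/60 against 12/120: p = 0.063
- one uncounted placebo infection instead, 13/60 against 10/120: p = 0.012

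A few uncounted infections can move the result across 5%, in a direction that depends on the arm they fall in.

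**4. Bias under a true null.** Take true risk p = 0.20 in both arms, a share w lost, and risk r × p in those lost. The observed risk is (p − w·r·p)/(1 − w) if they are dropped, and p − w·r·p if they are counted as uninfected. Differences are ciprofloxacin minus placebo.

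| Lost, cipro / placebo | r | Dropped | Counted uninfected |
|---|---|---|---|
| 5% / 15% | 2 | 0.1895 − 0.1647 = +2.5 points | 0.18 − 0.14 = +4.0 points |
| 5% / 15% | 0.5 | 0.2053 − 0.2176 = −1.2 points | 0.195 − 0.185 = +1.0 point |
| 10% / 5% | 2 | 0.1778 − 0.1895 = −1.2 points | 0.16 − 0.18 = −2.0 points |
| 5% / 5% | any | 0 | 0 |

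The sign changes with the pattern of loss and, in the second row, with the handling rule alone.

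**5. Power when withdrawn patients count as event-free.** Assume true risks of 20% (placebo) and 10% (ciprofloxacin), average BK risk in those withdrawn, and a share s of their events falling after withdrawal, with s from 0.5 to 0.75. Observed risk = true risk × (1 − w × s). Power is by exact enumeration at 120 against 60.

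| Withdrawn, placebo / cipro | Observed risks, s = 0.5 | Observed risks, s = 0.75 | Power |
|---|---|---|---|
| none | 20% v 10% | 20% v 10% | 46% |
| 5% / 5% | 19.5% v 9.75% | 19.25% v 9.63% | about 45% |
| 10% / 5% | 19.0% v 9.75% | 18.5% v 9.63% | 42% to 40% |
| 15% / 5% | 18.5% v 9.75% | 17.75% v 9.63% | 39% to 36% |

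Step 5 shows attenuation only. Step 4 shows what happens when those lost also differ in risk.

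**The case against.** The best case for the plan has five parts.

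- **Withdrawn subjects are still in the ITT set.** This stands. Someone off drug for 14 days has normally taken a dose. A reader might infer that the withdrawal rule removes such patients from the analysis set; 8.1.1 does not do that. The defect is a missing outcome, not an exclusion.
- **A late first dose does not exclude anyone.** This also stands. A reader might infer that a patient still in hospital after day 7 leaves the analysis. Section 8.1.1 asks for one dose, not one dose by day 7, so a late starter is a deviation from 6.4.1 who stays in. Only a patient who never starts is lost. With matching capsules and blinded staff, never starting is unlikely to depend on arm.
- **BK PCR is standard of care, so the outcome will be there anyway.** This stands in part. The scheduled PCRs make the remedy cheap, but 6.5.3 does not require them once a subject has withdrawn.
- **Section 9.2.1 need not end follow-up.** This is fair. Every subject stops drug by about day 90 and completers are followed to month 12, so the 30 days may be meant as a minimum. The section does not say so, and nothing else requires outcome visits from a withdrawn subject.
- **Withdrawal may be rare.** It is discretionary and needs a hold of more than 14 days. Drug can resume after quinolone treatment, 5.1.4.3 keeps subjects with BK viremia on drug except after an SAE, and fasting, another reason for a hold, has no obvious link to arm. The documents give no rates, so this can be neither confirmed nor dismissed.

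**Conclusion.** The point holds in two parts and should be dealt with. The dose requirement makes the set called ITT a modified ITT set. That is a mislabelling of probably small effect under blinding. The more important part is that the plan allows subjects off drug to leave before month 6, requires no BK PCR from them afterwards, and does not say how their missing outcome enters the chi-square test. One reason for leaving may differ by arm.

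The documents do not support a claim that the trial will be biased toward or against ciprofloxacin, or by how much. They give no number of never-dosed, held or withdrawn patients, and the sign of the illustrated bias depends on which arm loses more, on the risk of those lost, and on the handling rule. The power loss is modest unless withdrawal is clearly unequal: from 46% to about 45% at 5% in each arm, and to 36–39% at 15% placebo against 5% ciprofloxacin. The low starting power comes from the assumed 20% against 10% with 180 subjects and is a separate matter.

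**What to change.** 1. **8.1.1, analysis set.** Define ITT as all randomized subjects analysed in their assigned arm, and name it the primary set for the primary endpoint. Keep the dosed-only set, labelled modified ITT, as a sensitivity analysis.
2. **5.1.4.1, 5.1.4.2, 6.5.3 and 9.2.1, follow-up.** Separate decisions about study drug from participation in the study. Subjects off drug keep the scheduled BK PCRs (months 1, 2, 3, 6, 9 and 12) and outcome follow-up to month 12 unless they withdraw consent. This needs no change to any dosing or holding rule.
3. **8.1.1, missing outcomes.** State how a missing 6-month outcome enters the primary chi-square test, and add a sensitivity analysis under the alternative handling. This is needed even with the first two changes, because some subjects will withdraw consent or be lost.

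The cost is protocol and SAP wording, a little more follow-up and analysis work, and slight dilution of the estimate by undosed patients. The PCRs are already in the standard-of-care schedule, but obtaining them after drug is stopped would become a requirement instead of a possibility.
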